1. INTRODUCTION

During the first 12 weeks, pregnancy is carried out without significant blood flow from mother to the fetus. Later, fetal circulation in the developing tissues occurs at low oxygen pressure: in fetal blood, rarely pO₂ is higher than 30 mm/Hg. Therefore, from conception to delivery, the development of mammals occurs in hypoxia [1,2]. During delivery, infants are to cope with what could be defined as "*hyperoxic challenge*". The oxidative stress, that is the imbalance between oxidants and antioxidants in favor of the formers, affects tissues by producing free radicals. Extremely low birth weight infants (ELBW, birth weight lower than 1000 grams) are particularly sensitive to the oxidative stress, because of the immaturity of the antioxidant metabolic systems as well as the existence of frequent comorbidities, especially infections that, on their turn, increase the oxidative stress [3]. All the pathologies caused by the oxidative damage are defined as "oxidative stress-related diseases in newborns" [4,5]. These disorders, that are generally developed at the same time by the patient, include bronchopulmonary dysplasia (BPD), retinopathy of prematurity (ROP), necrotizing enterocolitis (NEC), periventricular leukomalacia (PVL) and, at least partially, intraventricular hemorrhage (IVH) [4,5]. EPICure (Extremely Premature Infant Cure) studies carried out in the United Kingdom showed that among premature infants born between the 22nd and the 26th gestational week, and with a postmenstrual age of 26 weeks, 68% of those who survived developed BPD, 21% were affected by ROP at least in one eye and 13% presented serious alterations during brain ultrasound scans [6,7]. Most recent papers described red blood cell transfusions as a main risk factor for the development of these pathologies [8-14] and the overall survival [14-16]. There are various factors explaining the correlation between the number of transfusions and the seriousness of the pathologies due to the oxidative damage, such as the immune modulatory effect (the term "transfusion-related immunomodulation" is used for the transfusion-related immunosuppression syndrome) [17,18] or the inflammation caused by "micro particles" that are released during the storage of red blood cells [19-21]. However, it is increasingly evident the role played by adult hemoglobin (HbA) that, due to its lower affinity to oxygen than fetal hemoglobin, greatly contributes to the oxidative stress [13,22,23]. The harmful role of HbA in preterm has clearly emerged in a recent prospective study, which showed that the incidence of ROP was inversely related to patients' fetal hemoglobin (HbF) levels, with a higher incidence among those showing the lowest levels [13]. In these patients, the level of HbF was obviously inversely proportional to that of HbA [13]. The current neonatal transfusion guidelines, by the Italian Society of Neonatology and the Italian Society of Transfusion Medicine, recommend the use of fresh leukoreduced red cell concentrates and the irradiation of blood components [24].

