with A-RBC. Overall, we transfused 23 UCB-RBC units and 27 A-RBC units. We observed that the two types of blood components led to a similar increase in the hematocrit levels and that the patients that were transfused with UCB-RBC or A-RBC received a similar number of transfusions at similar time intervals. There were no adverse events nor transfusion reactions and no CMV infections were recorded. In this limited number of patients, with an average follow-up of 57 days, the incidence of prematurity-related pathologies appeared to be globally comparable [46]. However, it was interesting to notice that the only two patients who did not develop ROP were only transfused with UCB-RBC [47]. More recently, a prospective study was carried out to show that the incidence of ROP was related to the levels of HbF in patients: the lower the levels, the greater the incidence [13]. Among those patients, the level of HbF was obviously inversely proportional to that of HbA. Therefore, even if it was a limited number of patients, the absence of ROP among the patients who were transfused with umbilical cord blood indirectly confirms the potentially damaging effect of adult blood transfusions [46, 47]. Our feasibility study also demonstrated that with current resources we are able to cover 50% of these patients' transfusion needs [46].

At global level, the implementation of a program for the transfusion of cord blood in a preterm infant could have an important clinical impact. Additionally, the introduction of this transfusion strategy could be an advantage in the rationalization of resources when using blood components. Actually, according to the criteria of cellularity established by the Italian Bone Marrow Donor Registry (IBMDR), less than 10% of cord blood units are cryopreserved and listed for transplants [48].

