4. TEST POPULATION

The study will include preterm infants who met the criteria of inclusion/exclusion and whose parents/tutors have given their informed consent. Based on the number of patients hospitalized every year in our NICU (roughly 150 patients/year) and the characteristics of the test population, we expect to achieve the sample size of 25 patients in 10 months.

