6. STATISTICAL CONSIDERATIONS

6.1 Definition of analysis sets

- **Enrolled (E) set or Intent-to-treat (ITT) analysis.** It will comprise all the enrolled patients, regardless of the administration or not of RBC transfusions.
- **Treated (T) set.** This group will comprise all the patients who were at least administered one transfusion, regardless of the completion of the observation period (36th week of PMA). Excluded from this set are the enrolled patients who were not transfused.
- **Per-Protocol (PP) set.** This group will comprise all the transfused patients who completed the observation period (36th week of PMA) or who died after completing it.

6.2 Calculation of sample size. The main goal of the study is to correlate the average HbF levels to the type of transfusion (UCB-RBC or A-RBC). With a population of 25 patients that will be studied during the following 8 weeks and a mortality rate of 1.9 patients/month, we expect to have 196 weekly doses of HbF to correlate to 98 transfusions. The total expected number of transfusion from birth to the completion of the 36th week of PMA was calculated to be around four transfusions per patient, with an UCB-RBC:A-RBC ratio of 1:1. In fact, for those patients with birth-determined characteristics similar to those of the studied population, the average number of transfusions within the 36th week of PMA is around 4 transfusions/patient [25], while in our previous study the average number of transfusions was 3 ± 1.7 [46]. In accordance with the literary data, preterm infants have an expected HbF concentration between 85% and 90% at birth and between 70% and 75% at the 36th week of PMA [54]. We expect that for the newborns who will not be transfused the HbF levels will stay in this range (70%-90%), while for the patients who will be transfused with adult red cells, HbA will dilute HbF. Even though there are no literary data yet, if we know the volume of transfused red cells (20 ml/kg) and the patient's blood volume, we can also assume that, for every adult red cell transfusion, HbF will be reduced by 15-20% compared to the pre-transfusion values until reaching levels lower than 20% among those patients who were transfused more than 4 times with adult blood.

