6.3 Statistical data analysis. The continuous variables will be expressed as mean (\pm SD) or as median (interquartile ranges, IQR); all deviations from normality will be detected with the Shapiro-Wilk test. The categorical variables will be expressed as n, (%), percentage). HbF levels in different type of transfusions will be compared in univariate analysis Mann-Whitney U test, end Kruskall Wallis test). Similarly, the transfusion efficacy analysis will be carried out based on a UCB-RBC and A-RBC non-inferiority study design by comparing the average time interval between two subsequent transfusions and the average post-transfusion capillary Ht

increase (Δ Ht) (Mann-Whitney U Test). The transfusion sample included in the study makes it possible to detect a difference between groups that is equal to at least 1 standard deviation with type I error $\alpha = 0.05$ and type II error $\beta = 0.2$ and a medium effect size (0.6). The correlation between the type of transfusion and other variables (prematurity related pathologies) will be tested using Fisher's exact test. Secondarily, in order to evaluate the effect of HbF reduction on the onset of prematurity-related pathologies, the levels of HbF levels will be inserted in a multiple linear regression model, by expressing the correlation between the onset of prematurity-related pathologies and the variables in terms of odds ratios (ORs \pm 90% confidence interval).

6.4 The primary outcome analysis will be tested on "E", "T" and "PP" sets. Transfusion efficacy outcome will be tested on "T" and "PP" sets.

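### The regression giving odds ratios for prematurity-related diseases has too few infants in the smaller outcome class for ordinary maximum likelihood, and section 6.3 sets neither a limit on predictors nor a small-sample method

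*Combined protocol and SAP*

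**What the plan says.** Section 2 lists as a secondary outcome the association between average HbF during the stay and ROP, BPD, NEC, PVL, IVH or death by 36 weeks of PMA. Section 6.3 supplies the model: HbF levels will be "inserted in a multiple linear regression model, by expressing the correlation between the onset of prematurity-related pathologies and the variables", with odds ratios and 90% intervals as the reported measure. No covariates are named. Section 5.9 records many candidates, including GA, birth weight, sex, ethnicity, twin birth, respiratory support, oxygen and antibiotic days.

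On size, section 4 states "we expect to achieve the sample size of 25 patients in 10 months". Section 6.2 counts measurements and transfusions: "we expect to have 196 weekly doses of HbF to correlate to 98 transfusions". The error rates and effect size in 6.3 are attached to the transfusion comparison. No count of diseased infants is given anywhere.

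The introduction is the only source of disease rates. For a UK cohort born at 22 to 26 weeks it reports that "68% of those who survived developed BPD, 21% were affected by ROP at least in one eye" and that "13% presented serious alterations during brain ultrasound scans". For the centre's own 20-infant pilot it reports that "the only two patients who did not develop ROP were only transfused with UCB-RBC". NEC and PVL have no rate.

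**The concern.** An odds-ratio model draws its information from the smaller of the two outcome classes, not from the number of HbF measurements. Each infant contributes one status per disease, however often HbF is measured. With a handful of infants in the smaller class and several predictors, some combination of predictors can split affected from unaffected infants perfectly. Maximum likelihood then has no finite solution. Short of that, the estimates scatter widely and lie too far from 1 when an effect exists.

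Section 10 presents this study as a possible basis for later randomised trials. An inflated odds ratio for HbF could mislead their planning.

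**Working it through.** **The plan's own figure.** Section 6.2 starts from this: "With a population of 25 patients that will be studied during the following 8 weeks and a mortality rate of 1.9 patients/month".
- 25 × 8 = 200 infant-weeks; 200 × (1 − 0.019) = 196.2.
- 25 × 4 = 100 transfusions; 100 × (1 − 0.019) = 98.1.

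So 196 and 98 both reproduce if 1.9 is used as a 1.9% loss. Taken as written, 1.9 per month over about two months is 3.8 deaths, leaving 25 − 3.8 = 21.2 infants. Neither 196 nor 98 is the sample size for the disease model, which is 25, or about 21.

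**Expected smaller class** = n × min(p, 1 − p).

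| Outcome | Rate | n = 25 | n = 21 | Per predictor, three predictors, n = 25 |
|---|---|---|---|---|
| BPD | 68% | 8.0 | 6.7 | 2.7 |
| ROP, UK cohort | 21% | 5.25 | 4.4 | 1.8 |
| Serious brain findings | 13% | 3.25 | 2.7 | 1.1 |
| ROP, pilot | 18/20 = 90% | 2.5 | 2.1 | 0.8 |

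The pilot rate assumes that all 20 infants were assessed for ROP, which the document does not state. A composite of any disease would be at least as common as BPD, so at these rates its smaller class is at most 25 × 0.32 = 8. At any rate whatever, 25 infants leave at most 12 in the smaller class.

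**How often maximum likelihood has no finite solution.** These are simulations at n = 25 with three predictors and essentially no HbF effect, with separation detected by linear programming where that was recorded. Covariates and their correlations are assumed, because the plan gives none.

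| Outcome | HbF plus two continuous covariates (such as GA, transfusion number) | HbF plus two covariates, one binary (such as sex) |
|---|---|---|
| BPD 68% | 0–1% | 3% |
| ROP 21% | 2–5% | 12% |
| Brain 13% | 12–17% | 31–36% |
| ROP 90% | 21–31% | 49–51% |

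A hand check explains the second column. If three infants form the smaller class, the chance that all are of one sex is 2 × 0.5³ = 25%; with two infants it is 2 × 0.5² = 50%. The percentages count fits in which at least one coefficient is infinite. When sex causes the separation, the HbF coefficient itself may stay finite.

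The number of predictors drives the result. With HbF and GA only, the figures are 0% (BPD), 1% (ROP 21%), 6% (brain) and 13% (ROP 90%). With HbF, GA, sex, birth weight and twin birth they are 11%, 32%, 58% and 69%.

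**Precision where the fit converges** (HbF, GA, sex; no true effect). The median ratio of upper to lower 90% limit is 6.8 (BPD), 8.9 (ROP 21%), 13.0 (brain) and 15.0 (ROP 90%). The HbF odds ratio per SD is at least 3 or at most 1/3 in these shares of converged fits:
- BPD: 0.117/0.972 = 12%
- ROP 21%: 0.162/0.880 = 18%
- Brain: 0.143/0.643 = 22%
- ROP 90%: 0.117/0.488 = 24%

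**Maximum likelihood against Firth** (HbF, GA, transfusion number). With no effect, the root mean squared error of the log odds ratio is 1.0–2.0 by maximum likelihood and 0.6–1.0 by Firth. With a true log odds ratio of −0.7 (odds ratio 0.50), maximum likelihood averages −1.0 to −1.3 (0.37 to 0.27). Firth averages −0.6 to −0.7 (0.55 to 0.50).

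**The case against.** The strongest reply is that the text names a linear model, and a linear model does not separate. That is so, but a linear model does not yield the odds ratios that the same sentence promises. This is a separate wording defect, and changing only the word to logistic would lead straight into the problem described here.

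The rates are also not planning assumptions. They come from infants of 22 to 26 weeks, whereas section 4.1.1 admits infants up to 30 weeks and/or up to 1000 g, and from one small pilot. This stands, and it makes the counts indicative only. The ceiling of 12 does not depend on any rate.

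A reader might infer that the plan fits one model per disease. Section 6.3 does not say so and could mean a composite, but the composite is no better placed at these rates.

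A reader might also infer that the model usually fails for every disease. The runs do not support that: for BPD, and mostly for ROP at 21%, it converges, and the trouble is imprecision. Nor is inflation shown when there is no effect; there the average log odds ratio stays near zero. Finally, nothing in the document says that results would be reported only where the software converges.

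The analysis is secondary, and section 6.3 already uses Fisher's exact test for transfusion type against disease. Both facts limit the weight of the point.

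**Conclusion.** The concern holds for the secondary disease model. At the only rates in the document, 25 infants give an expected smaller class of about 2.5 to 8. Ordinary maximum likelihood with three predictors then has a material risk of no finite solution for the rarer or near-universal outcomes: 12–36% for brain findings and 21–51% for ROP at the pilot rate. The risk is smaller for ROP at 21% (2–12%) and slight for BPD (0–3%). For all of them, converged estimates are very imprecise and, if HbF has a true effect, inflated away from 1.

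This rests on reading the model as logistic, on background rates, on all 20 pilot infants having been assessed for ROP, and on assumed covariates, whose choice accounts for much of the width of the ranges. It would be wrong to infer that the primary outcome is weakened; the HbF comparison at 32 weeks of PMA does not use this model. The change should be made, but the trial's main conclusion does not depend on it.

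**What to change.** In section 6.3, replace the multiple linear regression with Firth penalised logistic regression and profile penalised-likelihood intervals, one record per infant, for every modelled outcome. Enter HbF plus at most one or two covariates named in advance (for example GA), and label the analysis exploratory. State whether the outcome is each disease or a composite.

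Report the number affected and unaffected for every disease whether or not a model is fitted. Where the smaller class is too small to model, give only counts with exact intervals. Write that floor into the plan beforehand. The document does not determine it; a floor of 5, for instance, is a convention and would be expected to leave brain findings and ROP at the pilot rate unmodelled.

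The cost is SAP wording and standard software, with no extra infants or samples. The price is less covariate adjustment, and no adjusted odds ratio for the rarest or near-universal diseases. Firth stabilises the estimates but does not make 25 infants informative, so wide intervals should still be expected.

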7. DIRECT ACCESS TO DOCUMENTS AND DATA MANAGEMENT

The informed consents of both donor couples and enrolled patients' parents, as well as the data on the dosages on biological samples, will be available to the Ethical Committee. Nonetheless, the identity of the enrolled patients will be kept confidential and only the PI and his/her collaborators may have access to it.

8. ETHICAL ASPECTS

The study will be carried out according to the principles of Good Clinical Practice and the Declaration of Helsinki (Annex VI).

9. AUTHORIZATION OF THE ETHICAL COMMITTEE

Before beginning the study, the experimental design, consents and the related information material will be submitted to the Ethical Committee to approve it. Only after the Committee's approval will the study begin.

10. STUDY-RELATED RISKS AND BENEFITS

Due to the type of the patients, the volume of blood necessary to carry out the expected tests is a critical element. For this reason, the study was designed not to entail any more blood samples than those already taken to assist the patient. The HbF will be determined by using the capillary blood residue of other routine tests. As for the UCB-RBC transfusion, the immune

and infection risks are lower than A-RBC transfusions. Screening tests, adult and cord red cells production and storage techniques are comparable; the units of cord blood, unlike those of adult blood, are only released after checking the negativity of the microbial cultures. This procedure is due to the methods of cord blood collection and, if it guarantees sterility on the one hand, on the other, it prevents it from being transfused before five days have passed (i.e. the days necessary to detect any microbial contamination). This means that fetal blood transfusions could be less fresh than adult blood transfusions, even though a recent randomized study has not proven any remarkable differences in the safety and efficacy of the transfusions that were conserved for \pm 7 days [25]. Among the expected benefits of UCB-RBC transfusions is a lower risk of developing prematurity-related pathologies and the certainty that donors are CMV-negative.

This study could have a strong impact on the National Italian Health Service. In fact, it is only the first of many studies to test if the prevalence and seriousness of the prematurity-related pathologies can be reduced by applying an innovative transfusion approach, the aim of which is that of maintaining HbF at physiological levels during various weeks after birth. As far as we know, this approach has never been studied. It is also important to underline that the strategy of transfusing cord blood also has an economic impact since it is based on unused existing economic resources. Nowadays, Italian public Cord Blood Banks collect a very high number of CB units that cannot be used for transplants: in 2016, 14,661 CB units were collected but only 983 (6.7%) of them were listed for transplants.

The results of this study could be the assumption of many other randomized studies that aim to determine the negative impact of blood components on preterm infants and especially to establish if it can be a consequence of HbF reduction.

11. ADVERSE EVENTS

This single institution prospective study on the correlation between HbF and UCB-RBC or A-RBC transfusions is the first of its kind and all the adverse events occurring within the observation period will have to be carefully recorded. The researchers shall classify the adverse events (any signs or symptoms or diseases, including altered, unexpected or negative laboratory tests that are temporally related with the transfusion, regardless of their possible relation or not) as for:

- Seriousness (death, life-threatening, etc.);
- Intensity (severe, moderate, mild);

- Possible relation with the transfusion (not related, possibly correlated, probably related, definitely related);
- Outcome (resolved, resolved with sequelae, ongoing/continuing treatment, death).

12. SENSITIVE DATA AND BIOLOGICAL SAMPLES COLLECTION AND STORAGE

Data storage. The study PI will be in charge of storing an accurate recording of the transfusion procedures and clinical and laboratory data of the enrolled patients, as well as keeping the consents signed by the parents/tutors. Clinical data will be stored in electronic format for the following 10 years after the study termination. They will also have to include the recording of any adverse events that should occur during the study. There will also be specific consents for the treatment of personal data (Annex I bis).

Biological sample storage. In accordance with the Ethical Committee recommendations and pursuant to the authorization of the Italian Data Protection Authority to process generic data (February 22, 2007), samples will be identified anonymously and by using a numerical code. Only the physicians who are part of the study can trace the sample identity and the patient's clinical data through the number. The study PI will be in charge of storing the biological samples in the Cell Processing Laboratory of the Blood Transfusion Service. All the collected samples will only be used for the purposes of the study.

13. COMMITTEE IN CHARGE OF THE STUDY

The Committee in charge of the study will be composed of the study proposer, 3 neonatologists (1 coordinator and 2 supervisors), 3 hematologists (1 coordinator and 2 supervisors) and 3 members not directly involved in the study. This Committee will be in charge of monitoring the general aspects of the study and its possible reviews other than supervising and collecting data. The Committee will also be in charge of recording the clinical events that determine the end-points as well as the adverse events. It also has the power to make the necessary changes for potential alterations and corrections. Finally, any abstracts or manuscripts to submit to conferences also need the Committee's approval before they are published. The Committee will meet every three months, from the enrollment of the first patient to the study termination.

References

1. Maltepe E and Saugstad OD. *Pediatr Res.* 2009; 65:261-8.
2. Knuppel RA et al. (2012). Oxidative Stress and Antioxidants: Preterm Birth and Preterm Infants, Preterm Birth - Mother and Child, [name] (Ed.), ISBN: 978-953-307-828-1, InTech, Available from: <http://www.intechopen.com/books/preterm-birth-mother-and-child/oxidative-stress-and-antioxidants-preterm-birth-and-preterm-infants>.
3. Platt MJ. Outcomes in preterm infants. *Public Health.* 2014;128(5):399-403.
4. Saugstad OD. *Acta Paediatr* 1996; 85(1):1-4.
5. Saugstad OD. Oxidative stress in the newborn--a 30-year perspective. *Biol Neonate* 2005; 88:228-36
